6.3. Assessments and Evaluation of Response

The initial clinical evaluation will be conducted according to the standard practice. The investigator will perform a general examination of vital signs (blood pressure, heart rate, body temperature and respiratory rate) and complete physical examination during the initial visit, evaluation visits during treatment, and the final follow-up visit. Vital signs are to be measured according to standard clinical practice.

6.3.1. Processing blood samples and CSF

6.3.1.1. Blood Samples

Blood samples will be drawn at DHMC apheresis unit and collected and processed according to standard practice.

Blood samples to determine study parameters for biomarkers will be analyzed in research laboratories at local laboratory (DartLab) and by collaborating investigator [name] at the Institute for Ethnomedicine (Jackson Hole, Wyoming).

Amounts of blood/serum to be collected for each test are the following:

Test	Extraction Tube	Blood Volume (mL)	Comments
Biochemistry + Lipid Profile	Clotted blood	4	Analysis on site
Serum Electrolytes	Clotted blood	4	Analysis on site
Serology	Clotted blood	9	Analysis on site
Coagulation	Citrate	3	Analysis on site
Fibrinogen	Citrate	1	Analysis on site
Blood Count	EDTA K3	4	Analysis on site
Immune population profile	Na-Heparin	10	Analysis on site
Plasma retention sample	EDTA K2	4	Aliquots are stored at -80°C
Serology retention sample	SST II Advance	8.5	Aliquots are stored at -80°C

Test	Extraction Tube	Blood Volume (mL)	Comments
Biomarkers retention sample	EDTA K2	4	Plasma processing and aliquots of 1 mL are stored at -80°C
Cytokine panel + Neurofilament analysis	EDTA K2	5	Plasma processing and 1 mL aliquots are stored at -80°C
BMAA analysis	EDTA K2	5	Blood is to be spun down with serum and stored at -80°C

6.3.1.2. CSF Samples

Three (3) lumbar punctures will be performed according to standard of care at DHMC for obtaining CSF.

The CSF samples to determine safety parameters will be processed by local laboratory (DartLab) according to standard practice.

The CSF samples to determine study parameters for biomarkers will be analyzed by local laboratory (DartLab) and by collaborating investigator [name] at the Institute for Ethnomedicine (Jackson Hole, Wyoming).

The minimum recommended volume of CSF obtained from each lumbar puncture will be:

Test	Extraction Tube	Minimum CSF Volume (mL)	Comments
Standard Analysis (Cell count, glucose, total protein, and albumin levels)	Sterile tube	2	Analysis on site
CSF cytokine panel	Sterile tube	0.5	Aliquot is stored at -80°C
CSF Neurofilament analysis	Sterile tube	0.5	Aliquot is stored at -80°C
CSF BMAA analysis	Sterile tube	5	Aliquots are stored at -80°C
CSF retention sample	Sterile tube	1	Aliquot is stored at -80°C

6.3.1.3. Sample processing

Depending on the destination of the serum and/or plasma samples, samples should be analyzed on the same day (testing priority: coagulation, blood count, and biochemistry) or they may be stored at -80°C until analyzed (cytokine panel and BMAA).

Local DHMC hematological determinations will be performed in accordance with standard institutional practice. Before the analysis takes place, the samples may be kept at 2 to 8°C, except for the CSF samples, which will be kept at room temperature.

The plasma and CSF samples obtained for retention samples must be stored at -80°C. In the case of the CSF, the portion destined for standard analysis must not be frozen but should be kept at room temperature and analyzed immediately. The other portions may be frozen (rejecting further analysis if >10 erythrocytes are detected) or centrifuged prior to remove any residual cells.

The methods used for blood coagulation and for renal and liver function tests are those commonly used in the clinical laboratory of DHMC.

Clinical laboratory tests should be repeated at convenient intervals when abnormal results are obtained or if the investigator believes confirmatory tests are necessary; they should be repeated until the values become normal and stable. The investigator should explain all clinically relevant abnormal results.

Blood for immune population profiling and cytokine panels should be drawn \pm 2 hours from baseline time of draw due to circadian rhythms of leukocytes and cytokines.

6.3.2. ALS assessment scales

6.3.2.1. ALS Functional Rating Scale – Revised (ALSFRS-R):

This test is a validated rating instrument for progression of disability in ALS that provides an estimate of the degree of the subject's functional impairment through a short questionnaire. The ALSFRS-R has been widely used as a variable to determine the efficacy of a treatment or the progression of the disease.

The ALSFRS-R includes 12 questions to assess the level of self-sufficiency of subjects in various functional domains such as, bulbar function (questions 1-3), fine and gross motor function (questions 4-9), and respiratory function (question 10-12). Aspects of nourishment, personal care, personal autonomy, and communication are also evaluated. Each task is graded on a five point scale from 0 = is not able to do to 4 = normal ability. Individual scores are totaled to produce a final result of between 0 = worst and 48 = best.

See [APPENDIX 3. ALS Functional Rating Scale \(ALSFRS-R\)](#).

6.3.2.2. ALS Cognitive Behavioral Screen (ALS-CBS):

This test is designed as a screening tool to help identify subjects at risk for frontotemporal cognitive impairment and/or behavioral disorders. As such, this tool should not be used to establish a diagnosis, and a clinical neurological assessment will be required for diagnosis of ALS on all subjects prior to the test.

The test is composed by two sections. The first section is a 4 subdomain cognitive screening consisting of: Attention (complex orders, mental sums, language, and eye movement); Concentration (inversion of numeric series); Follow-up and monitoring (reverse sequences, alphabet, number and letter sequencing); and Initiation and Recovery (nomination). The second section consists of a questionnaire with 15 items of behavioral changes assessed by the caretaker.

The result of the cognitive section is a score of 0 to 20, based on the accuracy of the responses and the errors committed. The result of the behavioral section is the sum of the items on a Likert Scale.

See [APPENDIX 4. ALS Cognitive Behavioral Screen \(ALS-CBS\)](#).

6.3.2.3. ALS Assessment Questionnaire 40 (ALSA-Q40):

This specific ALS quality of life questionnaire provides insight on situations of great importance for ALS subjects in areas such as mobility, fear of falling when walking, difficulty eating and cutting, participation in meetings, feelings of isolation, embarrassing social situations, feelings of fear and hopelessness in the future, and problems associated with motor neuron disease.

The questionnaire consists of 40 items grouped into 5 representative dimensions associated

with quality of life: physical mobility (questions 1-10), activities of daily living (questions 11-20), food and drink (questions 21-23), communication (questions 24-30) and emotional function (questions 31-40).

Each item is scored from 0 to 4 according to a gradation of symptom onset frequency (never, rarely, sometimes, often, always). From raw scores, an index from 0 to 100 is obtained for each dimension, which make comparisons with the other dimensions possible as well as a straightforward interpretation of the results (0 = better state of health as measured by the questionnaire; 100 = poorer state of health). The first 4 scales refer to deficits and subsequent disabilities as a result of the disease. The fifth scale reflects how the subject is facing his/her physical deterioration emotionally.

See APPENDIX 5. ALS Assessment Questionnaire 40 (ALSA-Q40).

6.3.3. Respiratory Function Study

6.3.3.1. Forced Vital Capacity (FVC):

The FVC measures the volume of air that a person can forcibly exhale through a spirometer after a full inspiration. Following the the recommendations of the American Thoracic Society and European Respiratory Society this should be measured in a seated position, which facilitates subjects to be able perform multiple measurements if necessary. The result obtained is expressed in a percentage over the expected result in the general population.

6.3.4. Motor Function Study

6.3.4.1. EMG:

Surface EMG will be performed to record motor evoked potential in the distal muscles of the upper limbs (thenar and hypothenar eminence) and dorsiflexor muscles of the lower limbs (anterior tibialis) after electrical stimulation on the median, ulnar, and external popliteal sciatic nerve.

6.3.5. Determination of cytokine panel

To evaluate the role of neuro-inflammation and resident microglia in ALS subjects, levels of human ApoE (ApoE2, ApoE3, and ApoE4) and TGF β 1/2/3 in plasma and CSF will be measured by enzyme-linked immunosorbent assay (ELISA).(43,44) In addition, a human 14-plex Luminex assay for several inflammatory markers (IFN- γ , IL-1 β , IL-6, IL-10, IL-12p70, IL-17A, IL-17F, IP-10, MCP-1, MDC, MIP-1 α , MIP-1 β , TNF- α , sCD40L, and fractalkine) will be also performed.(45)

Plasma samples will be stored in aliquots at -80°C and cytokines will be assayed in a single batch after final visit (V6).

6.3.6. Immune population profile

Peripheral blood mononuclear cells (PBMC) profiles have been evaluated as a marker of disease stage and progression in ALS.(46) A significant decrease in CD14⁺CD16⁻ PBMC has been noted in ALS subjects.(47,48) PBMC have a pro-inflammatory profile in ALS, and there are fewer of these cells in the periphery in ALS.(49)

Lower amounts of regulatory T cells (Tregs) in periphery in ALS dampen the immune

response and activate cytotoxic T cells, microglia, and monocytes.(50,51) Circulating monocytes (CD14⁺CD16⁻) take up residence in the CNS and become microglia. In ALS, microglia adopt a pro-inflammatory (M1) phenotype, so do monocyte-derived macrophages that contribute to the resolution of the inflammatory response through secretion of IL-10 and chemokines (CCL17/CCL22) that recruit Tregs.(52) Tregs and myeloid-derived suppressor cells (MDSC) are both important to resolving inflammation.(53) Therefore, it is planned to characterize the immune population profile in ALS subjects assessed by flow cytometry following whole blood staining for the absolute leukocyte count (CD45, CD3, CD4, CD8, CD19, CD14, CD56, and CD16); MDSC population (CD15, CD124, lineage, CD33, HLA-DR, CD14, CD11b, and CD45); Treg population (CD3, CD4, CD25, CD39, CD45, CD127, CD152, and FoxP3) and monocytes (CD11b, CD14, CD16, CD45, CD163, FcεR1alpha, and CX3CR1).

Immune population profile plasma samples will be assayed within 4 hours of blood draw.

6.3.7. Neurofilament proteins

A histopathological hallmark of ALS is the accumulation of neurofilaments (NFs) and ubiquitinated inclusions inside motor neurons.(54-56) NFs are major structural elements of the neuronal cytoskeleton and are composed of three different polypeptides: light, medium, and heavy subunits. Levels of NFs will be measured by ELISA.

Plasma samples will be stored in aliquots at -80°C and neurofilament proteins will be assayed in a single batch after last visit (V6).

6.3.7.1. Phosphorylated Neurofilament heavy chain (pNF-H)

pNF-H is elevated in subjects with ALS, and some studies suggest that levels may change over the course of disease.(56-58) pNL-H is the potential biomarker closest to validation in the ALS field. The main body of evidence for pNL-H in CSF suggests that it could be used as a diagnostic biomarker to differentiate those who have ALS versus those who do not. Less clear is the possible role of pNL-H as a prognosis biomarker.

6.3.7.2. Neurofilament light chain (NF-L)

NF-L is a main break down product of neurodegeneration, which is considered to reflect axonal damage, and it has been reported to be variably elevated in small cross-sectional studies in blood and CSF in ALS subjects.(59,60) Moreover, immunoreactivity to plasma NF-L is informative of the stage of disease progression in ALS, and thus it has been postulated as a potential biomarker with prognostic value.(61) NF-L changes are less validated but could be informative of the effect of the treatment on disease progression.

6.3.8. β-methylamino-L-alanine (BMAA) analysis

BMAA is a non-proteinogenic amino acid produced by cyanobacteria and has been shown to be present in the brain of subjects who subsequently develop ALS.(62,63) BMAA is incorporated in place of L-serine into different neuroproteins, causing misfolding and formation of tangles. It has been demonstrated that BMAA replaces L-serine by attaching to the serine tRNA. When a peptide bond forms between BMAA and the adjacent amino acid, the resultant protein is kinked and misfolded.(64)

To assess the role of BMAA in ALS subjects, different tests will be conducted in this study

using both plasma and CSF samples.

Blood serum will be stored in aliquots at -80°C and will be analyzed using triple quadrupole LC/MS/MS for BMAA levels in a single batch after last visit (V6). In addition, complete amino acid profiles of selected samples will be performed with post-column ninhydrin derivatization in a Hitachi Amino Acid Analyzer.

CSF samples will be stored in aliquots at -80°C and will be hydrolyzed and then derivatized with AQC (6-aminoquinolyl-N-hydroxysuccinimidylcarbamate) in preparation for triple quadrupole LC/MS/MS analysis. If CSF volume permits, complete amino acid profiles of selected samples will be produced through post-column derivatization with ninhydrin using the Hitachi Amino Acid Analyzer.

6.3.8.1. BMAA levels:

Measuring levels of BMAA at baseline and over the course of treatment at each evaluation visit can identify reductions in BMAA levels, which could potentially be correlated with disease progression or a halt in disease progression. Analysis will be performed using a Thermo TSQ Quantiva triple quadrupole mass spectrometer on AQC-derivatized samples of blood serum and CSF. Where sample volume permits, complete amino acid profiles will be performed using a Hitachi amino acid analyzer set for physiological fluids (see [section 6.3.8.2](#)).

6.3.8.2. L-serine levels:

L-serine levels will be determined in CSF and plasma as a potential indicator of BMAA replacement for L-serine. Analysis will be performed using a Hitachi amino acid analyzer set for physiological fluids at the Institute for Ethnomedicine Research Center, as well as with a Thermo TSQ Quantiva triple quadrupole mass spectrometer.

7. ASSESSMENT OF SAFETY

7.1. Adverse Events

7.1.1. Warnings/Precautions

As shown in the current package insert, the most serious ARs are anaphylactic shock, heart failure, and pulmonary edema. The most common ARs are anaphylactoid type reactions.

Adverse reactions to Albutein 5% normally resolve when the infusion rate is slowed or the infusion is stopped. In case of severe reactions, the infusion is stopped and appropriate treatment initiated.

The following ARs have been identified during post approval use of human albumin, including Albutein (all strengths) in decreasing order of significance: anaphylactic shock, heart failure, pulmonary edema, hypotension, tachycardia, vomiting, urticaria, rash, headache, chills, fever, flushing, and nausea.

The expected events related to PE are: [\(65,66\)](#) hypocalcemia (manifested by paresthesias, headaches, visual disturbances, nausea, cramps, and chest tightness) and coagulation disorders due to dilution of coagulation factors (mainly hypofibrinogenemia, with the possibility of observing minor bleeding associated with severe thrombocytopenia). Hypotension may be experienced (accompanied by pallor, sweating, bradycardia, nausea,

vomiting, syncope, sphincter relaxation, and seizures) although the risk is minimal since an amount equivalent to that extracted is infused. It is also possible to experience allergic reactions (hives, dyspnea, wheezing, hypotension, tachycardia, flushing, and eyelid edema). Other events may have a psychological origin or be inherent to the process, for example, pain after being immobilized several hours.

7.1.2. Adverse Event Monitoring

Subjects must be carefully monitored for AEs. This monitoring includes clinical and laboratory tests and physical signs. AEs should be assessed in terms of their seriousness, severity, and causal relationship to the investigational product.

The investigator is responsible for the detection and documentation of events that comply with the criterion and definition of an AE or a serious adverse event (SAE), in accordance with that set forth in this protocol. AEs and SAEs will be documented from the time the subject signs the informed consent before the first PE and until the subject returns for the last study visit, whether the subject has completed the study or has stopped prematurely for any reason.

7.1.3. Adverse Event Definitions

7.1.3.1. Adverse Events

An AE is defined as any untoward medical occurrence in a patient or clinical investigation subject administered a medicinal product or study treatment and which does not necessarily have a causal relationship with this administration. An AE may therefore be any unfavorable and unintended sign (including any abnormal laboratory finding, for example), symptom, or disease temporally associated with the use of a medicinal product, whether or not considered related to the medicinal product.

Baseline manifestations of the illness itself or its logical progression directly related to the course of the illness itself are not considered to be AEs, such as muscle weakness, abnormal muscle movements (e.g., twitching, clonus, or cramps), or an abnormal loss of muscle mass or body weight, breathing difficulties, emotional lability, and difficulty speaking and/or swallowing, which are considered bulbar manifestations of the underlying disease.

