More recently, in 2008 a clinical case was reported involving a patient with elevated anti-phospholipid antibody titers who was diagnosed as definite ALS based on the revised El Escorial criteria.(18) The patient was simultaneously treated with 50 cc/kg/day PE for 5 days and 50 mg/day prednisolone, followed by treatment with oral prednisolone alone, and reducing the dose gradually to 10 mg/day. An improvement in the ALS symptoms was observed in this patient after 3 months with the combined PE and prednisolone treatment.

In 2013, at the ALS Multidisciplinary Unit of the Hospital Universitari de Bellvitge (Barcelona,

Spain), 2 ALS patients were treated with PE with Albutein 5% in a compassionate use program. The regimen used was 3 PEs per week during the first 2 weeks followed by 1 PE per week for the following 12 weeks. In each procedure, 110% of the plasma volume was processed. Apart from the onset of asthenia (lack of strength), both patients tolerated the treatment well, and a stabilization of symptoms measured by the amyotrophic lateral sclerosis functional rating scale - revised (ALSFRS-R) functional scale was observed in 1 of the 2 patients on 2 occasions during the treatment period.

Given the results in the above mentioned cases, the researchers felt it would be of interest to evaluate the efficacy of PE with Albutein 5% in ALS in an experimental context since it has been more than 30 years since the last publication with PE for ALS. Since then, knowledge of the disease has increased together with the reliability of tools to measure disease progression. In the same way, PE procedures are increasingly being used and are currently considered a safe medical intervention thanks to the technical improvements of the apheresis machines and the thorough management of patients within the apheresis units.

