7.1.3.8 Laboratory tests and other physical evaluation abnormalities

A laboratory test abnormality considered clinically relevant, e.g., causing the subject to withdraw from the study, requiring treatment or intervention, causing apparent clinical manifestations, or judged relevant by the investigator, should be reported as an AE. Each

event must be described in detail along with start and stop dates, severity, relationship to investigational product, action taken, and outcome. Each event must be adequately supported by documentation as it appears in the subject's medical or case file.

Other abnormal test (e.g., neurological, physical examinations, functional tests) that worsen from the start and are considered clinically relevant, they should also be recorded as an AE.

The investigator shall apply their medical criteria on deciding whether the abnormal findings are important medical events as defined in [section 7.1.3.6](#).

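### The adverse event definition leaves out signs attributed to ALS without an attribution rule, overlaps with listed plasma exchange reactions for cramps and dyspnea, and conflicts with sections 6.2.3 and 7.1.3.8

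*Protocol*

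**What the plan says.** Protocol section 7.1.3.1 first defines an AE broadly, "whether or not considered related to the medicinal product". It then makes an exception: "Baseline manifestations of the illness itself or its logical progression directly related to the course of the illness itself are not considered to be AEs". The examples follow at once: "such as muscle weakness, abnormal muscle movements (e.g., twitching, clonus, or cramps), or an abnormal loss of muscle mass or body weight, breathing difficulties", then emotional lability and difficulty in speaking or swallowing.

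Section 7.1.1 gives the expected effects of the exchange. They include "hypocalcemia (manifested by paresthesias, headaches, visual disturbances, nausea, cramps, and chest tightness") and "allergic reactions (hives, dyspnea, wheezing, hypotension, tachycardia, flushing, and eyelid edema"). Section 1.2 reports on the two ALS patients treated under compassionate use: "Apart from the onset of asthenia (lack of strength), both patients tolerated the treatment well".

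Two other sections set recording rules. Section 6.2.3 requires that, before each PE, any abnormality seen since baseline or the last procedure is entered as an AE. Section 7.1.3.8 says of abnormal neurological, physical and functional tests "that worsen from the start and are considered clinically relevant, they should also be recorded as an AE". Neither makes an exception for ALS.

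Section 6.1.3 and SAP section 4.3 include as a safety variable the percentage of PE sessions with at least one AE, whatever its cause, during the infusion or in the 72 hours after it.

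**The concern.** A cramp or breathlessness after an exchange may come from the exchange or from ALS. The protocol lets the investigator settle that question at the recording step, with no criterion of timing, onset or rate of change. If the answer is ALS, the event never reaches the AE page, and the session AE percentage is filtered by presumed cause although it is defined to ignore cause. The error runs in one direction, toward a safer-looking procedure. The trial is open-label with one arm, so no control rate can show afterwards how many such events were due to treatment. Events that were not recorded cannot be recovered from the AE data.

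**Working it through.** The plan gives no figure to reproduce. The check is a comparison of texts, with simple arithmetic for scale.

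**1. Which signs are on both lists?**

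| Sign | 7.1.3.1: example of ALS, not an AE | 7.1.1: listed reaction |
|---|---|---|
| Cramps | yes | yes, with hypocalcemia |
| Breathing difficulty | yes | yes, as dyspnea and wheezing with allergic reaction |
| Muscle weakness | yes | no; only asthenia in section 1.2 |
| Weight loss, swallowing difficulty | yes | no |
| Chest tightness | no | yes, with hypocalcemia |

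The named overlap is cramps and breathing difficulty. The albumin reactions in 7.1.1 include pulmonary edema and heart failure, but that list does not name breathing difficulty itself.

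**2. In what order are the decisions made?** Section 7.1.2 limits documentation to events that meet the AE definition. The causality grading in 7.1.3.3 has a safeguard: if a link to treatment cannot be ruled out, the event may not be called unrelated. Its category of possible is written for events that the patient's clinical state could also explain. Both apply only to an event already accepted as an AE. The exclusion in 7.1.3.1 comes first, so it can remove the very events that the category of possible is meant to hold. SAP section 6.3.8 adds no rule that settles this.

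**3. Do the recording rules agree?** Take two cases.

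- A new leg cramp on the evening after a session. Under 7.1.3.1 it is not an AE if judged to be ALS. Under 6.2.3 it is an AE at the next session. Section 7.1.3.8 is silent, because this is a symptom and not a test finding.
- Loss of strength on the week 12 neurological examination, considered clinically relevant. Under 7.1.3.1 it is not an AE if judged to be progression. Under both 6.2.3 and 7.1.3.8 it is one.

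The rules give opposite answers in both cases.

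**4. How often could ALS signs fall inside a 72-hour window?** Inputs are 6 sessions in 3 weeks and 21 sessions in 21 weeks (section 5.1), and 10 subjects (section 4.3).

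- Sessions: 10 × (6 + 21) = 270 at most.
- Window days per subject: 27 × 3 = 81 of 24 × 7 = 168, or 48%.
- Intensive phase: 6 × 3 = 18 of 21 days, or 86%.
- Maintenance phase: 21 × 3 = 63 of 147 days, or 43%.

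The day counts are upper limits, because windows can overlap when sessions are 48 hours apart. They leave out the sessions themselves.

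**5. What would under-recording do?** The documents give no rates, so these are assumptions. Let t be the true share of sessions with an AE, and s the share of those sessions whose only events are overlap signs left unrecorded as ALS. The recorded share is t × (1 − s).

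| t | s = 10% | s = 25% | s = 50% |
|---|---|---|---|
| 10% | 9% | 7.5% | 5% |
| 20% | 18% | 15% | 10% |
| 30% | 27% | 22.5% | 15% |

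**The case against.** The strongest reply is that the exclusion is conditional. It reaches only what is directly related to the course of ALS, so a cramp from hypocalcemia or dyspnea from an allergic reaction remains an AE. That is correct, and a reader who infers a blanket exclusion of weakness, cramps and breathing difficulty goes beyond the text. What remains is the ambiguous case, for which the condition has no test.

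The protocol also has safeguards. Calcium and other electrolytes are measured after each session, and vital signs and pulse oximetry before, during and after it (6.2.3). New symptoms during PE are assessed by a research nurse (5.2). Clinically relevant laboratory and vital-sign changes are AEs (11.4). These make it less likely that a clear reaction in the unit is missed. The scheduled measurements end 15 to 30 minutes after the procedure, however, and most of the 72 hours lies beyond that. Section 6.2.3 itself pushes toward recording, but it does so by contradicting 7.1.3.1.

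Three further inferences are not supported:

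- That weakness is a listed reaction. It is in neither list in 7.1.1; the only related evidence is asthenia in two patients.
- That 7.1.3.8 contradicts the exclusion for every symptom. It covers test and examination findings considered clinically relevant.
- That faster decline caused by treatment would go unseen. ALSFRS-R and FVC are the primary variables, SAP section 6.3.4 compares ALSFRS-R change with the expected loss of 1 point per month, and the neurological examination is tabulated by visit.

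The percentage of sessions with an adverse reaction should hardly move either. That term needs a causality of definite, which an event mistaken for ALS would rarely reach.

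**Conclusion.** The point holds as a defect in the recording rules. Sections 7.1.3.1, 6.2.3 and 7.1.3.8 give different answers for the same event. The ALS exclusion has no attribution rule, acts before causality grading, and overlaps with the listed PE reactions for cramps and dyspnea. The variable exposed is the all-cause percentage of sessions with an AE. The direction of bias is toward under-reporting wherever 7.1.3.1 is followed over 6.2.3; if practice varies, recording is also inconsistent between subjects and visits. The size is unknown. The 48% coverage shows only that ambiguous timing will be common, and the recorded shares in the working rest on assumed values, so neither is an estimate of events lost.

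**What to change.** Reconcile 7.1.3.1, 6.2.3 and 7.1.3.8 into one recording rule, and repeat it in the CRF guidance:

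- Any new or abruptly worse sign with onset during a PE or within 72 hours after it is recorded as an AE, however much it resembles ALS. Its cause is handled in the 7.1.3.3 grading.
- Outside that window, gradual progression in line with the subject's prior course is captured by ALSFRS-R, FVC and the neurological examination and is not an AE. Sections 6.2.3 and 7.1.3.8 are amended to say so. The ALSFRS-R and FVC values from the 6 months before enrollment, which 6.2.2 collects where possible, help to describe that course.

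In SAP section 6.3.8, tabulate treatment-emergent AEs and session AE percentages with and without a prespecified list of ALS-type terms, namely the signs named in 7.1.3.1.

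The cost is protocol and CRF wording, a few extra tables, more AE entries and a somewhat higher reported AE rate. Treatment and visit schedules do not change. The recording rule helps only with events observed after it takes effect.
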